2.2.2 Primary Endpoint(s)

The study has two co-primary endpoints that both have to succeed.

Incidence Rate of FVIII-inhibitors ≥ 0.6 BU

The rate of inhibitors will be reported and a 1-sided 97.5% upper confidence limit will be provided based on an exact calculation for a binomial distribution. For the calculation of the inhibitor rate the nominator will include all patients with neutralising antibodies while the denominator will include all patients with a minimum of 50 exposures plus any patients with less than 50 exposures but with neutralising inhibitors. Adequate safety with regard to neutralising inhibitors will be concluded if the upper 1-sided 97.5% confidence limit is below 6.8% roughly corresponding to the upper 97.5% confidence limit if 2 inhibitors out of 105 patients are observed (3 or less if the study should get 127 or more patients with 50 exposure days).

Annualised bleeding rate (total number of bleeding episodes per patient assessed as annualised bleeding rate) in the prophylaxis arm

A review of historical data has found that haemophilia A patients on on-demand treatment on average bleed 24 times per year while they bleed 6.8 times per year when treated on prophylaxis.

Historical Control for Hypothesis Test for Prophylaxis

Based on the studies referenced below, Novo Nordisk suggests that representative numbers for mean annual bleeding rate (ABR) in severe haemophilia patients is 24 bleeds/year for patients treated on-demand and 6.8 for patients on prophylactic treatment.

Novo Nordisk has based the estimate of historical annual bleeding rate on a systematic review of the treatment of Haemophilia A and B and von Willebrand disease, performed by the Swedish Council on Health Technology Assessment.

The referenced report is based on review of 3710 abstracts in total, covering treatment of Haemophilia A, B or von Willebrand disease. Articles were then selected for full review according to specific criteria such as administration of recombinant or plasma-derived Factor concentrate, outcome (eg number of bleeding episodes, inhibitor development or quality-of-life measurements), and number of patients included. For haemophilia A, only studies comprising 20 patients or more were selected. The main objectives of the SBU review is to evaluate the short- and long-term effects

with different treatment strategies with coagulation factor concentrates in Haemophilia A and B and von Willebrand disease.

In the search, SBU identified 37 references dealing with “replacement therapy with factor concentrates in treating severe, moderate, and mild haemophilia A”. All these references identified by SBU were reviewed as full length articles at Novo Nordisk, and only the original papers with a mean total ABR reported (or at least possible to calculate) in patients with an endogenous FVIII:C activity <2% were included in our analysis.

Table 2–1 Historical mean total annual bleeding rate in Haemophilia A patients with an endogenous FVIII:C activity <2%

SBU Ref No	Reference	On-demand (mean ABR)	Number of patients	Prophylaxis (mean ABR)	Number of patients
4	Courter, 2001³	18	27	4	27
5	Lusher, 2003⁴	23	85	10	85
5	Lusher, 2003⁴	N.R.	N.R.	6	45
9	Tarantino, 2004⁵	N.R.	N.R.	6.3	107
10	Nemes, 2007⁶	N.R.	N.R.	4.9	49
11	Recht, 2009⁷	N.R.	N.R.	3.9	94
15	Abshire, 2000²	34	38	8.3	27
17	Smith, 2005^{*8}	N.R.	N.R.	10.3	32
18	Manco-Johnson, 2007¹	18	33	3.3	32
25	Schwartz, 1990^{**9}	19	56	N.R.	N.R.
	Weighted Mean	24	179	6.8	394

ABR = Annual Bleeding Rate. N.R. = not reported. Studies in *italics* have not included adults. No = Reference number in SBU report, chapter 3.1.1. * 5/32 are moderate Hemophilia A, **4/56 are moderate Hemophilia A

In the studies, the mean ABR in patients on prophylaxis is consistently lower than in patients treated on-demand, as expected. The studies have ABR in the range of 18 – 34 and 3.3 – 10, for on-demand and prophylaxis treatment, respectively, and include different numbers of subjects. To arrive at a representative ABR number from the various studies, we weighted the estimates from each study based on the number of subjects included.

As the proposed trial with N8-GP will only include patients aged 12 years and above, we further suggest to exclude 3 of the 9 historical studies^{1,3,4}, that only include children below age 6, in order to better reflect the study population. The historical mean ABR for on-demand and prophylaxis in haemophilia A with <2% will then be estimated at 24 and 6.8, respectively. However, if also the

studies including children below 6 years of age are included, the estimated ABR for on-demand and prophylaxis are 23 and 6.4, respectively. The 2% cut off is often used in clinical studies and will give a conservative estimate of the ABR in the study population in the proposed trial with a cut off of <1%.

Prophylactic effect of N8-GP will be concluded if the bleeding rate is significantly below 50% of the historical on-demand bleeding rate (i.e. significantly lower than 12) as well as within 25% of the historical prophylaxis bleeding rates (i.e. significantly lower than $6.8 * 1.25 = 8.5$). Since both must be met in practice it must be shown that the bleeding rate is significantly lower than 8.5.

Let AR be the true yearly bleeding rate. The null-hypothesis will be tested against the alternative hypothesis as given by:

$H_0: AR \geq 8.5$ against $H_A: AR < 8.5$

The endpoint will be analysed by a Poisson regression model on number of bleeding episodes per patient allowing for over-dispersion (using Pearson's chi-square divided by the degrees of freedom (i.e. $Scale = P_{scale}$ in SAS)) and using log observation duration as an offset. Estimates of the annualised bleeding rates will be provided with 95% confidence intervals.

For patients withdrawing prematurely, the number of bleeding episodes counting in the analysis will be imputed up to what they could be expected to have had if they had completed the trial. If e.g. a patient withdraws after 2 months with 3 bleeding episodes, but the patient should have been in the study for 12 months, then this patient will in the analysis count as having had 18 bleeding episodes in 12 months. This is similar to last observation carried forward (LOCF) and will avoid positive bias occurring from patients with many bleeding episodes withdrawing early.

The rules for calculating planned exposure time used for imputation depends on what part of the trial the patient is withdrawn from and furthermore what parts of the trial the calculations represent as described in the following.

Calculations of ABR for the Pivotal part:

Since the planned exposure time for each patient in the Pivotal phase of the trial depends on when the patient was recruited in the trial, the maximum expected exposure time based on the last visit date included in each part of the analysis will be used as planned exposure time, e.g. the date of the last patient's first visit after his 50EDs will be used for the pivotal part of the analysis where all patients should have reached at least 50 EDs (except for patients having had surgery as part of pathfinder™3).

Calculations of ABR for extension phase part 1:

For patients who were withdrawn in the Pivotal part the planned exposure time will be until the end of the pivotal part as described above. For patients who were withdrawn in the main part after the pivotal part ended, the maximum expected exposure time will be used, i.e. 100 weeks as this is the maximum duration for main phase. For patients withdrawn during extension phase part 1, the planned exposure is 24 weeks (duration of extension phase part 1) added to the actual exposure in main

For calculations only including the randomised period, the planned exposure time will be the time from visit 14 to visit 17, i.e. 24 weeks. Patients that change from Q7D to non-randomised part of Q4D will have their bleeds imputed using a planned exposure time of 24 weeks using the same approach as in the pivotal part of the trial even though they are not withdrawn from the study. This is to avoid bias for randomized Q7D caused by patients withdrawing due to high bleeding rate.

Calculations of ABR for extension phase part 2:

For patients withdrawn prior to extension phase part 2, planned exposure is calculated as explained above. For patients withdrawing during extension phase part 2, planned exposure in extension phase part 2 will be calculated using the overall cut-date (15Aug2017) as planned end date. The actual exposure time in main and extension phase part 1 is added to the planned exposure time in extension phase part 2, to get the overall planned exposure time for a withdrawn patient.

Planned exposure time is only relevant for the treatment regimen the patient is on, when being withdrawn. Time on other regimens and time in surgery trial is subtracted when calculating planned exposure time.

For patients who withdrew within 1 month, imputation will be conducted by assuming an annualised bleeding rate of 24 (bleeds per year) for the missing period. This also applies to change from Q7D to Q4D in the randomised part of extension phase part 1.

Estimates of the annualised bleeding rates for each regimen will be provided together with the 95% confidence intervals as described in the protocol.

Sensitivity analyses:

Analysis applying a different model

A sensitivity analysis based on a negative binomial regression model with number of bleeding episodes requiring treatment as the outcome variable, and adjusting for exposure time will be performed.

Analysis without imputation to planned trial duration

The primary prophylaxis analysis will be repeated but without imputing number of bleeding episodes for any withdrawals. Instead only the observed bleeding episodes will be counted and the offset will be actual observation duration rather than planned.

Analysis imputing by LOCF without imputation for withdrawals occurring within the first month

The primary analysis will be repeated but without using imputation of 24 bleeding episodes for withdrawals within the first month. Instead only the observed bleeds and the observed duration will be used for such subjects.

Analysis imputing a minimum of 24 bleeds per year to planned trial duration

A conservative sensitivity analysis will be performed imputing for all withdrawals the observed bleeding rate into the missing period if it is greater than 24 per year and otherwise 24 per year. As an example a patient with 3 bleeds in 2 months (observed ABR 18) that should have been in the study for 12 months will have 20 bleeds imputed for the missing 10 months. Patients with 6 bleeds in 2 months (observed ABR 36) will have 30 bleeds imputed into the missing 10 months.

Analysis of 12 months data from patients that could have had 12 months prophylaxis

Since patients will stay in the Main Phase of the trial until the same end of Main Phase date some patients will get only about 7 months prophylactic treatment while others may get more than 19 months (except for patients entering the trial with the intention of major surgery after the end of normal recruitment period). To investigate if the varying durations have any impact on the results a sensitivity analysis will be performed looking only at 12 months data from patients with planned trial duration of 12 or more months. Otherwise this analysis will be performed similarly to the primary analysis. This sensitivity analysis is not applicable after the interim for extension phase, part 1, since no new data for the main phase and extension phase part 1 will be available.

To investigate the effect over time the bleeding rates per month will be calculated and summarised numerically and graphically. This will be done by treatment regimen and only including the first consecutive period on each treatment regimen. A patient that is on different treatment regimens during the trial will therefore have bleeding rate per month calculated for each treatment regimen, but only including the first consecutive period on each treatment regimen. Surgery leave is not considered change in treatment regimen.

Similarly the bleeding rate by calendar month will be calculated and presented. If there is a calendar effect it is conceivable that it would be reversed in the southern hemisphere compared to the

northern. Therefore, calendar months for Australia and Brazil are shifted 6 months, i.e. January is changed to July, February to August etc.

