2.2 Section 1 Summary

Trial Population:

Foot note added: *An “exposure day” is defined as any day the patient has been exposed to N8-GP including on demand, prophylaxis, during surgery and in PK sessions. If N8-GP is administered more than once during the same day, this will still count as one exposure day*

Key Inclusion criteria:

Age ≥ 12 years and body weight ≥ 35 kg (except for Croatia, ~~and~~ The Netherlands *and France* where the lower age limit will be 18 years)

2.3 Section 2

Table 2–1 Flow Chart for Patients on Prophylaxis and On-Demand Treatment

‘X’ has been added to the follow-up visit in the flowchart to indicate that N8-GP binding antibodies must be measured.

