2.2 Statistical Methods

2.2.1 General Considerations

Novo Nordisk A/S will be responsible for the statistical analysis. All tests will be performed as 1-sided tests on 2.5% significance level. All bleeding endpoints will be evaluated based on bleeding episodes requiring treatment with N8-GP. Non-treatment requiring bleeding episodes that coincide with regular prophylaxis doses are not included in the analyses.

Multiple bleeding locations occurring from the same event (e.g. due to a bicycle accident) or at the same time point will be counted as one bleeding episode and only one haemostatic response will be considered for the bleeding episode. In case different responses were registered for different bleeding locations in such a bleeding episode, the worst response will be used in the analysis. As stated in the protocol, a re-bleed is defined as a worsening of symptoms in the same location after an initial period of improvement, either on treatment or within 72 hours after stopping treatment. If a bleed occurs in the same location later than 72 hours after stopping the treatment it is

considered a new bleed. Re-bleeds will only be considered for joint bleeds since the specific location for other bleeds e.g. in subcutaneous are not captured in the database.

In the sub analyses of annualised bleeding rate where there are less than 5 patients in a sub-group, model based estimation will not be done. If no bleedings occur in a sub-group, then the confidence interval will not be calculated.

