2.5 Interim Analysis

All data from the Main Phase of the trial will be analysed and reported when all patients have reached at least 50 EDs (except for patients having had surgery as part of pathfinder™3), and all patients have had their first visit after 50 EDs where all planned assessments including inhibitors have been performed. The analysis of the main phase of the trial will be based on all data up to the patient's last visit at this point. All main conclusions from the trial will be based on this reporting.

Furthermore, an interim analysis was performed when all patients had completed extension phase part 1. The interim for the extension phase part 2 will cover all data from the main phase and extension phase 1+2 up to last visit before 15-Aug-2017.

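### The inhibitor denominator counts patients with 50 exposures without requiring an inhibitor test after the 50th, so a patient who withdraws before his next sample enters as inhibitor-free; the effect is always favourable but decides the verdict only at the boundary counts

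*SAP*

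**What the plan says.** SAP 2.2.2, repeating Protocol 18.2.2, puts every patient with neutralising antibodies in the numerator. For the denominator, "the denominator will include all patients with a minimum of 50 exposures plus any patients with less than 50 exposures but with neutralising inhibitors". The analysis is exact: "a 1-sided 97.5% upper confidence limit will be provided based on an exact calculation for a binomial distribution". The criterion follows: "Adequate safety with regard to neutralising inhibitors will be concluded if the upper 1-sided 97.5% confidence limit is below 6.8"%. The same sentence describes this margin as "roughly corresponding to the upper 97.5% confidence limit if 2 inhibitors out of 105 patients are observed", and relaxes the acceptable count to "3 or less if the study should get 127 or more patients with 50 exposure days".

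A test after 50 exposure days (EDs) is mentioned elsewhere, as a timing condition. SAP 2.5 has the Main Phase analysed once "all patients have had their first visit after 50 EDs where all planned assessments including inhibitors have been performed". SAP 2 and Protocol 18.5 (Amendment 14) carry the same clause. It decides when the report is made. It does not decide who is counted.

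The Protocol Summary footnote added by Amendment 6 defines an exposure day as any day with exposure to N8-GP, "including on demand, prophylaxis, during surgery and in PK sessions", and counts several doses on one day as one exposure day. The denominator sentence speaks of exposures; the 127-patient rule in the same paragraph speaks of exposure days.

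**The concern.** The estimate is meant to be the inhibitor rate in patients followed through at least 50 EDs. A patient is informative for that only if someone looked for an inhibitor after the 50th ED, and the sponsor's own timing condition recognises this. The denominator rule does not carry the requirement over and gives no instruction for a patient who has 50 exposures but no later sample. Since he is not in the numerator, he counts as a negative.

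Such a patient adds one to the denominator and nothing to the numerator, so he can only lower the rate and its upper limit. The endpoint is one of two that must both succeed, and the 6.8% criterion was set so that 2 of 105 just passes. A small number of unsupported negatives could therefore matter if the observed count falls on the boundary.

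**Working it through.** **Inputs.** One-sided 2.5% level (SAP 2.2.1); exact binomial upper 97.5% limit, criterion below 6.8%, 2 of 105 and 3 of 127 acceptable (SAP 2.2.2); dosing every 4 days (Protocol 5.3.1); visits at weeks 4, 8, 12, 20, 28 and 36 (Protocol Table 2-1); antibody samples taken pre-dose (Protocol 8.3.2); enlarged target of 145 prophylaxis completers (Amendment 10); assumed true inhibitor rate 0.5% (Protocol 18.1, Amendment 6).

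**Formula.** Upper limit for x inhibitors in n patients = 97.5% quantile of Beta(x + 1, n − x).

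**Plan's own figures reproduced.**
- 2/105: 6.71%, passes; 3/105: 8.12%, fails.
- 3/127: 6.75%, passes; 3/126: 6.8005%, fails. The threshold of 127 is exact.
- Power for at most 2 inhibitors among 132 at a true rate of 0.5%: 97.1%, against the stated 97%.

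**Can the situation arise?** On a strict 4-day schedule starting on day 0, the 50th dose falls on day 49 × 4 = 196, which is week 28, the nominal date of Visit 7. The sample at that visit is drawn before the dose, so without extra bleed doses it follows only 49 exposures. The next scheduled sample is Visit 8, eight weeks later. For a patient withdrawn in between, Protocol 8.1 asks the investigator to aim at the last-visit procedures if possible. If they are not done, he has 50 exposures and no later test. By schedule he does have five earlier on-treatment tests (Visits 3 to 7).

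The on-demand sampling rule opens no separate gap: samples are skipped only when there was no treatment since the last visit, so a patient whose 50th ED fell between visits is due a sample at the next one.

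**Effect of removing patients with no test after the 50th ED.**

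| Inhibitors | Starting n | Limit at start | Smallest n that passes | Limit there | Limit one lower | Removals to fail |
|---|---|---|---|---|---|---|
| 0 | 105 | 3.45% | 53 | 6.72% | 6.85% | 53 |
| 1 | 105 | 5.19% | 80 | 6.77% | 6.85% | 26 |
| 2 | 105 | 6.71% | 104 | 6.77% | 6.84% | 2 |
| 3 | 127 | 6.75% | 127 | 6.75% | 6.8005% | 1 |
| 3 | 145 | 5.93% | 127 | 6.75% | 6.8005% | 19 |

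Removals to fail = starting n − (smallest passing n − 1); for example, 105 − 103 = 2.

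**How likely is the boundary?** At the protocol's assumed rate of 0.5%, a binomial count in 105 patients equals exactly 2 with probability 8.1%, and equals 0 or 1 with probability 90.2%.

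**The case against.** The strongest reply is that the gap is narrow and mostly closed elsewhere. Inhibitors are sampled at every scheduled visit except 2b, Main Phase reporting waits for the visit after 50 EDs, and Protocol 8.1 wants every attempt made to arrange an end visit, which includes an inhibitor sample. What remains requires a withdrawal after ED 50, before the next sample and without an end visit. Nothing in the documents shows that one such patient exists. The rule also leans the conservative way in one respect: it adds inhibitor patients below 50 exposures and leaves out negatives below 50. All of this stands.

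Three stronger readings are tempting and are not supported.

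- A reader might infer that untested patients are counted as negatives. These patients have about five on-treatment tests; what is missing is the last window, at most about eight weeks on the nominal schedule.
- A reader might infer that surgery-trial patients are exempt from the post-50 test. The bracketed exception in SAP 2.5 and Protocol 18.5 attaches to reaching 50 EDs, not to the clause about the later visit. Returning surgery patients resume at the next visit in line, the surgery trial's end-visit assessments are used, and Visit 13 must precede the extension (Protocol 8.1.6, renumbered 8.1.7).
- A reader might infer that two patients are enough to change the verdict in general. That holds only with exactly 2 inhibitors in 105.

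It is also fair to say that the SAP is dated January 2019 and describes the pivotal part as already reported, so a new definition cannot pre-specify that verdict. And since the success rule and the protocol's sample-size text use exposure days, an analyst would probably read exposures in that sense.

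What the reply does not remove is that the counting rule itself still lacks the test, and that SAP 2.10 re-evaluates the inhibitor rate on accumulated data without restating a denominator, so the SAP 2.2.2 wording governs there too.

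**Conclusion.** The point holds as a gap in the endpoint definition, not as evidence that the reported result is wrong. The denominator should itself contain the post-50-ED test that the reporting condition presupposes. Patients who continue are covered by that condition; patients who withdraw after ED 50 without a later sample are not, and each of them moves the limit in the favourable direction. Their number is not given and is probably small.

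The size depends entirely on the observed count. At 2 in 105, two such patients turn a pass into a fail, while one does not. At 3 in 127, one does. At 0 or 1 in 105, or 3 in 145, a handful makes no difference. At 3 in 105 the criterion already fails. These figures assume that the affected patients are removed from the denominator and that the numerator is unchanged. The timing argument assumes strict 4-day dosing and nominal visit dates; extra doses for bleeds bring the 50th ED earlier and make a sample after it more likely. This is a cheap improvement worth making.

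**What to change.** In SAP 2.2.2, and in Protocol 18.2.2 if it is amended again, define the denominator as patients with at least 50 exposure days and at least one central-laboratory inhibitor test after the 50th exposure day, plus every confirmed inhibitor patient. Use exposure days throughout.

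Apply this to the accumulated inhibitor analysis in SAP 2.10. Report the current denominator as a sensitivity analysis and list the patients removed, with the date of the last test and the exposure days at that test. Show the already reported pivotal result under the new definition as a supplementary check, labelled as such.

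The cost is one sentence, one listing and one extra row in a table. The denominator may lose a few patients and the upper limit becomes slightly less favourable; for example, losing one of 105 with 2 inhibitors raises it from 6.71% to 6.77%. If nobody is removed, that is worth stating, because it closes the question.
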